3.3.2 Exclusion Criteria

1) Target Disease Exceptions

- a) Lymphomas and Multiple Myeloma.
 - i) Subjects with primary cutaneous lymphoma, lymphoproliferative diseases associated with primary immune deficiencies, and lymphomas associated with human immunodeficiency virus (HIV) infection are excluded.
 - ii) Solitary bone or solitary extramedullary plasmacytoma as the only evidence of plasma cell dyscrasia.
 - iii) Monoclonal gammopathy of undetermined significance (MGUS), smoldering myeloma or Waldenström's macroglobulinemia.
 - iv) Active plasma cell leukemia (defined as either 20% of peripheral WBC comprised of plasma/CD138+ cells or an absolute plasma cell count of 2×10^9 /L).
- b) Subjects with known or suspected central nervous system (CNS) metastases or with the CNS as the only site of active disease are excluded:
 - i) Subjects with controlled brain metastases will be allowed to enroll. Controlled brain metastases are defined as those with no radiographic progression for at least 4 weeks after radiation or surgical treatment at the time of consent. Subjects must have been off steroids for at least 2 weeks prior to informed consent and have no new or progressive neurological signs and symptoms.
 - ii) Subjects with signs or symptoms of brain metastases are not eligible unless brain metastases are ruled out by computed tomography (CT) or magnetic resonance imaging (MRI).

2) Medical History and Concurrent Diseases

- a) Subjects with a prior malignancy are excluded, except adequately treated basal cell or squamous cell skin cancer, carcinoma in situ of the cervix or of the bladder, or in situ ductal or lobular carcinoma of the breast. Subjects with other prior malignancies diagnosed more than 2 years previously (at the time of informed consent) who have received therapy with curative intent with no evidence of disease during the interval and who are considered by the Investigator to present a low risk for recurrence will be eligible.
- b) Subjects with an active, known or suspected autoimmune disease. Subjects with type I diabetes mellitus, hypothyroidism only requiring hormone replacement, skin disorders (such as vitiligo, psoriasis, or alopecia) not requiring systemic treatment, or conditions not expected to recur in the absence of an external trigger are permitted to enroll. Subjects with well-controlled asthma and/or mild allergic rhinitis (seasonal allergies) are eligible.
- c) Subject has autoimmune hemolytic anemia (AIHA) or autoimmune thrombocytopenia (ITP) requiring therapeutic doses of systemic steroids.

- d) Subject has undergone any allogeneic transplant.
- e) Subject has received autologous/allogeneic T-cells transfer.
- f) A known or underlying medical condition that, in the opinion of the Investigator or Sponsor, could make the administration of study drug hazardous to the subject or could adversely affect the ability of the subject to comply with or tolerate study procedures and/or study therapy, or confound the ability to interpret the tolerability of relatlimab in treated subjects.
- g) Requirement for daily supplemental oxygen.
- h) Uncontrolled or significant cardiovascular disease including, but not limited to, any of the following:
 - i) Myocardial infarction (MI) or stroke/transient ischemic attack (TIA) within the 6 months prior to consent.
 - ii) Uncontrolled angina within the 3 months prior to consent.
 - iii) Any history of clinically significant arrhythmias (such as ventricular tachycardia, ventricular fibrillation, or torsades de pointes).
 - iv) QTc prolongation > 480 msec.
 - v) History of other clinically significant cardiovascular disease (ie, cardiomyopathy, congestive heart failure with New York Heart Association [NYHA] functional classification III-IV, pericarditis, significant pericardial effusion, significant coronary stent occlusion, deep venous thrombosis, etc).
 - vi) Cardiovascular disease-related requirement for daily supplemental oxygen.
 - vii) ***Not applicable per Revised Protocol 07. See criteria xi) below for cardiac troponin.*** Cardiac Troponin T (cTnT) or I (cTnI) $\geq 2 \times$ institutional ULN. Subjects with cTnT or cTnI levels between > 1 to $2 \times$ ULN will be permitted if repeat levels within 24 hours are ≤ 1 ULN.
 - (1) If cTnT or cTnI levels are > 1 ULN at 24 hours, the subject may undergo a cardiac evaluation and be considered for treatment, following a discussion with the BMS Medical Monitor or designee.
 - viii) History of myocarditis, regardless of etiology.
 - ix) History of two or more MIs or two or more coronary revascularization procedures.
 - x) A confirmed history of encephalitis, meningitis, or uncontrolled seizures in the year prior to informed consent.
 - xi) Troponin T (TnT) or I (TnI) $> 2 \times$ institutional ULN.

Note: Subjects with TnT or TnI levels between > 1 to $2 \times$ ULN will be permitted if repeat levels within 24 hours are $\leq 1 \times$ ULN. If TnT or TnI levels are > 1 to $2 \times$ ULN within 24 hours, the subject may undergo a cardiac evaluation and be considered for

treatment, following a discussion with the BMS Medical Monitor or designee. When repeat levels within 24 hours are not available, a repeat test should be conducted as soon as possible. If TnT or TnI repeat levels beyond 24 hours are $< 2 \times$ ULN, the subject may undergo a cardiac evaluation and be considered for treatment, following a discussion with the BMS Medical Monitor or designee.

- i) Positive blood screen for HIV or known acquired immunodeficiency syndrome (AIDS).
- j) Any positive test result for hepatitis B virus or hepatitis C virus indicating presence of virus, eg, Hepatitis B surface antigen (HBsAg), Australia antigen) positive, or Hepatitis C antibody (anti-HCV) positive (except if HCV-RNA negative).
- k) Evidence of active infection that requires systemic antibacterial, antiviral, or antifungal therapy ≤ 7 days prior to initiation of study drug therapy.
- l) Any other significant acute or chronic medical illness.
- m) Subjects who are unable to undergo venipuncture and/or tolerate venous access.
- n) Any other sound medical, psychiatric, and/or social reason as determined by the Investigator.
- o) Subjects with history of life-threatening toxicity related to prior immune therapy (eg, anti-CTLA-4 or anti-PD-1/PD-L1 treatment or any other antibody or drug specifically targeting T-cell co-stimulation or immune checkpoint pathways) except those that are unlikely to re-occur with standard countermeasures (eg, hormone replacement after endocrinopathy).
- p) Any of the following procedures or medications:
 - i) Within 2 weeks prior to study drug administration:
 - (1) Subjects with a condition requiring systemic treatment with either corticosteroids (> 10 mg daily prednisone equivalent) or other immunosuppressive medications within 14 days of relatlimab administered as monotherapy or in combination with nivolumab. Inhaled or topical steroids, and adrenal replacement steroid doses > 10 mg daily prednisone equivalent, are permitted in the absence of active autoimmune disease.
 - ii) Within 4 weeks prior to study drug administration:
 - (1) Any investigational drug or placebo.
 - (2) Any anticancer therapy (IMiDs [eg, lenalidomide], proteasome inhibitors, chemotherapy, monoclonal antibody for antineoplastic intent [eg, anti-CTLA-4, anti PD-1, anti PL-1, anti PDL-2, anti-CD20, anti-CD30, or alemtuzumab antibody therapy], therapeutic vaccines, radiotherapy, or hormonal treatment).
 - (3) Non-oncology vaccines containing live / attenuated virus within 30 days of first treatment.
 - (4) Allergen hyposensitization therapy.
 - (5) Major surgery.

iii) Within 6 weeks prior to study drug administration:

(1) Nitrosureas, fludarabine.

iv) Within 10 weeks prior to study drug administration:

q) Radio-immunoconjugates.

3) Allergies and Adverse Drug Reaction

a) History of allergy to anti-PD-1 or anti-PD-L1 antibody therapy or to other monoclonal antibodies or related compounds or to any of their components (eg, history of severe hypersensitivity reactions to drugs formulated with polysorbate 80).

4) Other Exclusion Criteria

- a) Prisoners or subjects who are involuntarily incarcerated (Note: under specific circumstances, and only in countries where local regulations permit, a person who has been imprisoned may be included as a participant. Strict conditions apply and Bristol-Myers Squibb [BMS] approval is required).
- b) Subjects who are compulsorily detained for treatment of either a psychiatric or physical (eg, infectious disease) illness.
- c) Inability to comply with restrictions and prohibited activities/treatments as listed in [Section 3.4](#).

Eligibility criteria for this study have been carefully considered to ensure the safety of the study subjects and that the results of the study can be used. It is imperative that subjects fully meet all eligibility criteria.

3.3.3 *Women of Childbearing Potential*

A woman of childbearing potential (WOCBP) is defined as any female who has experienced menarche and who has not undergone surgical sterilization (hysterectomy or bilateral oophorectomy) and is not postmenopausal. Menopause is defined as 12 months of amenorrhea in a woman over age 45 in the absence of other biological or physiological causes. In addition, women under the age of 55 must have a serum follicle stimulating hormone (FSH) level > 40 mIU/mL to confirm menopause.

Females treated with hormone replacement therapy, (HRT) are likely to have artificially suppressed FSH levels and may require a washout period in order to obtain a physiologic FSH level. The duration of the washout period is a function of the type of HRT used. The duration of the washout period below are suggested guidelines and the investigators should use their judgement in checking serum FSH levels. If the serum FSH level is >40 mIU/mL at any time during the washout period, the woman can be considered postmenopausal.

- 1 week minimum for vaginal hormonal products, (rings, creams, gels).
- 4 week minimum for transdermal products.
- 8 week minimum for oral products.

Other parenteral products may require washout periods as long as 6 months.

3.4 Concomitant Treatments

3.4.1 Prohibited and/or Restricted Treatments

The following medications are prohibited during the study:

- Immunosuppressive agents unless they are utilized to treat an AE or as specified in [Section 3.4.3](#).
- Concurrent administration of any anticancer therapies (investigational or approved) with the exception of subjects in the survival period of the study.
- Use of allergen hyposensitization therapy.
- Use of growth factors unless prior discussion and agreement with BMS Medical Monitor.
- Use of cannabis or other recreational drugs.
- Any live / attenuated vaccine (eg, varicella, zoster, yellow fever, rotavirus, oral polio and measles, mumps, rubella [MMR]) during treatment and until 100 days post last dose.

Palliative radiotherapy is permitted only under certain conditions as described in Section 3.4.3.

3.4.2 Other Restrictions and Precautions

3.4.2.1 Vaccinations

Any vaccination containing attenuated or inactivated virus may be permitted if clinically indicated. However, this must be discussed and documented with the BMS Medical Monitor **prior to administration** and may require a study drug washout period prior to and after administration of the vaccine. Inactivated influenza vaccination will be permitted on study without restriction. Any vaccination containing live virus is prohibited.

3.4.2.2 Imaging Restrictions and Precautions

It is the local imaging facility's responsibility to determine, based on subject attributes (eg, allergy history, diabetic history and renal status), the appropriate imaging modality and contrast regimen for each subject. Imaging contraindications and contrast risks should be considered in this assessment. Subjects with renal insufficiency should be assessed as to whether or not they should receive contrast and if so, what type and dose of contrast is appropriate. Specific to MRI, subjects with severe renal insufficiency (ie, estimated glomerular filtration rate [eGFR] $< 30 \text{ mL/min/1.73 m}^2$) are at increased risk of nephrogenic systemic fibrosis. MRI contrast should not be given to this subject population. In addition, subjects are excluded from MRI if they have tattoos, metallic implants, pacemakers, etc.

The ultimate decision to perform MRI in an individual subject in this study rests with the site radiologist, the investigator and the standard set by the local Ethics Committee.

3.4.3 Permitted Therapy

Subjects are permitted the use of topical, ocular, intra-articular, intranasal, and inhalational corticosteroids (with minimal systemic absorption). Immunosuppressive agents and the use of systemic corticosteroids are permitted in the context of treating AEs, prophylaxis prior to a diagnostic procedure (eg contrast MRI/CT scans) or as specified in [Section 3.4.4](#). A brief course of corticosteroids for prophylaxis (eg, contrast dye allergy) is permitted after discussion with the BMS Medical Monitor.

Subjects may continue to receive HRT.

Oral antiviral therapy (acyclovir or equivalent) may be required to reduce the risk of herpes zoster reactivation. Discussion with medical monitor is required for any subject planned to receive oral anti-viral therapy.

Palliative and supportive care for disease-related symptoms may be offered to all subjects on the trial; however, Investigators should consult with the BMS Medical Monitor prior to initiating palliative radiation in subjects who have not yet completed the DLT evaluation interval (Part A).

The potential for overlapping toxicities with radiotherapy and relatlimab administered as monotherapy or in combination with nivolumab is currently not known. Therefore, palliative radiotherapy is not recommended while receiving any of these drugs, alone or in combination. If palliative radiotherapy in short courses and for isolated fields is required to control symptoms not clearly related to disease progression, then drug administration should be withheld, if possible, for at least 1 week before radiation and for at least 2 weeks after its completion. Subjects should be closely monitored for any potential toxicity during and after receiving radiotherapy. Prior to resuming study drug treatment, radiotherapy-related AEs should resolve to \leq Grade 1 or baseline and subjects must meet relevant eligibility criteria as determined by the BMS Medical Monitor in discussion with the Investigator. The BMS Medical Monitor must be consulted prior to re-initiating treatment in a subject with a dosing interruption lasting > 6 weeks after the last dose.

Details of palliative radiotherapy should be documented in the source records and electronic case report form (CRF). Details in the source records should include dates of treatment, anatomical site, dose administered and fractionation schedule, and AEs. Symptoms requiring palliative radiotherapy should be evaluated for objective evidence of disease progression. Administration of additional relatlimab, as monotherapy or in combination with nivolumab to subjects who receive limited-field palliative radiation, should follow guidelines specified in [Section 4.3.5](#). Subjects receiving palliative radiation of index lesions will have the evaluation of ORR just prior to radiotherapy but such subjects will no longer be evaluable for determination of response subsequent to the date palliative radiation occurs.

For subjects who need to undergo elective surgery (not tumor-related) during the study, it is recommended to hold study drug for at least 2 weeks before and 2 weeks after surgery, or until the subject recovers from the procedure, whichever is longer. Prior to resuming study drug treatment, surgically related AEs should resolve to \leq Grade 1 or baseline and subjects must meet relevant eligibility criteria as determined by the BMS Medical Monitor in consultation with the

Investigator. The BMS Medical Monitor must be consulted prior to re-initiating treatment in a subject with a dosing interruption lasting > 6 weeks after the last dose.

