8.3.2.3 Efficacy

All efficacy analyses will be based on the all treated analysis population except otherwise stated. Co-primary, secondary and exploratory efficacy endpoints for Part D subjects are as follows:

Objective Response Rate (ORR)

ORR based on investigator assessment, according to the applicable criteria based on tumor type, will be co-primary endpoint in Part D. For the NHL and HL subjects, the ORR will be based on the IWG (2007) response criteria. In addition to the primary ORR endpoint, an exploratory endpoint of ORR based on the Lugano (2014) response criteria in the NHL and HL subjects in Part D will be assessed. For the Lugano criteria, response is defined as CMR and PMR.

Duration of Objective Response (DOR)

DOR is defined as the time between the date of first documented response (CR or PR) to the date of the first objectively documented progression as per criteria relevant to each disease type in Part D (Appendices 1, 2, and 6), or death due to any cause, whichever occurs first. For subjects who neither progress nor die, DOR will be censored on the date of their last tumor assessment. Subjects who start subsequent therapy without a prior reported progression will be censored at the last tumor assessments prior to initiation of the subsequent anticancer therapy. This endpoint will only be evaluated in subjects with objective response of CR or PR. DOR will be evaluated based on investigator assessments. DOR is a co-primary endpoint in Part D. DOR based on the Lugano (2014) response criteria, response defined as CMR or PMR, will be assessed for the NHL/HL subjects in Part D as an exploratory endpoint.

Complete Response (CR) Rate and Duration

The CR rate is defined as the number of subjects with a best overall response (BOR) of CR according to the applicable criteria based on tumor type, based on IWG criteria for NHL and HL subjects, divided by the number of treated subjects. The duration of CR (DoCR) will only be evaluated in subjects with BOR of CR and is defined as the time from first documentation of CR (the date of first negative FDG-PET scan) to the date of initial objectively documented progression as determined using the applicable criteria based on tumor type or death due to any cause, whichever occurs first. Censoring will be applied as per DOR definition. CR rate and DoCR will be evaluated based on investigator assessments. CR rate is an exploratory endpoint in this study.

Progression Free Survival (PFS) Rate

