PFS is defined as the time from first dose to the date of first objectively documented progression, per applicable criteria based on tumor type or death due to any cause, whichever occurs first. Subjects who die without a reported progression will be considered to have progressed on the date of their death. Subjects who did not progress or die will be censored on the date of their last evaluable tumor assessment. Subjects who did not have any on study tumor assessments and did not die will be censored on the date of first dose. Subjects who started any subsequent anti-cancer therapy, including tumor-directed radiotherapy and tumor-directed surgery, without a prior reported progression will be censored at the last evaluable tumor assessment prior to initiation of the subsequent anti-cancer therapy. The PFS rate at time T is defined as the probability that a subject has not progressed and is alive at time T following first dose. PFSR will be assessed at Weeks 16, 24, 32, 40, and 100, and evaluated based on investigator assessments. PFS will be an exploratory endpoint in this study.

Overall Survival (OS) Rate

OS is defined as the time between the date of first dose and the date of death. For subjects without documentation of death, OS will be censored on the last date the subject was known to be alive. The overall survival rate at time T is defined as the probability that a subject is alive at time T following first dose OS will be assessed at various time points in HL patients in Part D.

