APPENDIX 1 2007 INTERNATIONAL WORKING GROUP (IWG) RESPONSE CRITERIA FOR MALIGNANT LYMPHOMA

2007 IWG Response Criteria for Malignant Lymphoma ¹				
Response	Definition	Nodal masses	Spleen, Liver	Bone marrow
CR	Disappearance of all evidence of disease	(a) FDG-avid or PET positive prior to therapy; residual mass of any size permitted if PET negative (b) Variably FDG-avid or PET negative; regression to normal size on CT	Not palpable, nodules disappeared	Infiltrate cleared on repeat biopsy; if indeterminate by morphology, immunohistochemistry should be negative
PR	Regression of measurable disease and no new sites	≥ 50% decrease in SPD of up to 6 largest dominant masses (index lesions); no increase in size of other nodes (non-index lesions) (a) FDG-avid or PET positive prior to therapy; one or more PET positive at previously involved site (b) Variably FDG-avid or PET negative; regression on CT	≥ 50% decrease in SPD of nodules (for single nodule in greatest transverse diameter); no increase in size of liver or spleen	Irrelevant if positive prior to therapy; cell type should be specified
SD	Failure to attain CR/PR or PD	(a) FDG-avid or PET positive prior to therapy; PET positive at prior sites of disease and no new sites on CT or PET (b) Variably FDG-avid or PET negative; no change in size of previous lesions on CT	N/A	N/A
Relapsed disease or PD	Any new lesion or increase by ≥ 50% of previously involved sites from nadir	Appearance of a new lesion(s) > 1.5 cm in any axis, ≥ 50% increase in SPD of more than one node (index lesions), or ≥ 50% increase in longest diameter of a previously identified node > 1 cm in short axis. Lesions PET positive if FDG-avid lymphoma or PET positive prior to therapy	> 50% increase from nadir in the SPD of any previous lesions	New or recurrent involvement

Key: CR = complete remission, CT = computed tomography; FDG = [18F] fluorodeoxyglucose; IWG = International Working Group; NA = Not applicable; PD = progressive disease; PET = positron-emission tomography; PR = partial remission; SD = stable disease; SPD = sum of the product of the diameters.

¹ Cheson, BD, Pfistner, B, Juweid, ME, et al. Revised criteria for malignant lymphoma. *J Clin Oncol.* 2007; 25:579.

CR (Complete Remission)

The designation of CR requires the following:

APPENDIX 1 Complete disappearance of all detectable clinical evidence of disease and disease-related symptoms, if present before therapy.

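### After palliative radiotherapy, response evaluation stops only if an index lesion was irradiated, and DOR censoring does not name radiotherapy as PFS censoring does

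*Combined protocol and SAP*

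**What the plan says.** **Radiotherapy on study.** Section 3.4.1 refers the reader on: "Palliative radiotherapy is permitted only under certain conditions as described in Section 3.4.3". Section 3.4.3 then discourages it ("palliative radiotherapy is not recommended while receiving any of these drugs, alone or in combination"), confines it to a narrow case ("If palliative radiotherapy in short courses and for isolated fields is required to control symptoms not clearly related to disease progression"), and asks for a check first: "Symptoms requiring palliative radiotherapy should be evaluated for objective evidence of disease progression". Study drug is held around the course if possible and may be resumed.

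**Response.** Section 3.4.3 gives one analysis rule: "Subjects receiving palliative radiation of index lesions will have the evaluation of ORR just prior to radiotherapy". Those subjects cannot be evaluated for response after the radiation date. Subjects irradiated only at non-index sites are not mentioned. The ORR and CR rate definitions in Section 8.3.2.3 set no cut-off at radiotherapy, surgery or later therapy.

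**Appendix 1 (2007 IWG).** PR needs at least a 50% fall in the SPD of up to six dominant masses and also "no increase in size of other nodes (non-index lesions". CR needs every detectable sign of disease to be gone.

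**Durations (Section 8.3.2.3, and the same in the synopsis).** For DOR, a Part D co-primary endpoint: "Subjects who start subsequent therapy without a prior reported progression will be censored at the last tumor assessments", the assessments meant being those before the later anticancer therapy. For PFS: "Subjects who started any subsequent anti-cancer therapy, including tumor-directed radiotherapy and tumor-directed surgery, without a prior reported progression will be censored". DoCR and DoCMR take over the DOR rule. Lugano PFS takes over the PFS rule (Section 8.3.3.3).

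**The concern.** The plan accepts that radiotherapy confounds response, but acts on this for only part of the disease that decides response. Part D cohorts have no control arm and response is assessed by the investigator, so nothing else in the design separates a radiotherapy effect from a drug effect.

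The two duration rules stand next to each other and list different therapies. Two programmers could reasonably handle the same subject in different ways. At stake are the co-primary ORR and DOR, and the CR rate, which Section 8.1.3 makes the yardstick for anti-PD-1/PD-L1-naive HL.

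**Working it through.** The documents give no figure on this point, and the Part D sample sizes and rates are redacted. The check is mainly a comparison of text, with illustrations on assumed inputs.

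**Step 1. What irradiating a non-index site can do under Appendix 1**

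| Status before radiotherapy | Possible status after a non-index site is irradiated | Endpoint affected |
|---|---|---|
| Index SPD down by less than 50% | No PR from this alone, because the SPD fall is measured on index lesions | None |
| Index SPD down by at least 50%, non-index node growing but short of PD | PR, once the growth is reversed | ORR, and entry into the DOR set |
| PR, with a non-index node the only remaining disease | CR, if that site clears | CR rate and DoCR; ORR unchanged |

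In rows 2 and 3 the rule in Section 3.4.3 leaves the subject evaluable.

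**Step 2. Size for ORR.** One added response shifts the rate by 100/n points. For assumed n = 10, 15, 20, 30, 40 this is 10.0, 6.7, 5.0, 3.3, 2.5 points. In the synopsis, the stage 1 futility guidance for anti-PD-1/PD-L1-progressed HL is triggered by having no response at all, so there a single response matters.

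**Step 3. One subject under the two duration rules.** Assume scans every 8 weeks, PR at Week 8, a non-index site irradiated at Week 20, study drug resumed, and progression at Week 60.

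- Radiotherapy treated as censoring therapy for PFS only: PFS censored at Week 16; DOR an event at 60 − 8 = 52 weeks.
- Treated as censoring therapy for both: PFS censored at Week 16; DOR censored at 16 − 8 = 8 weeks.
- Treated as censoring therapy for neither: PFS an event at Week 60; DOR an event at 52 weeks.

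The text does not choose among these. The first is what results if on-study radiotherapy is censored only where it is named.

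**Step 4. Direction of the effect on DOR**

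*Radiotherapy delays progression and is unrelated to prognosis (assumed).* Simulated exponential DOR, 400,000 responders per setting; 5, 10 or 20% irradiated at month 3 if still responding; progression delayed by 3 or 6 months.

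| True median (months) | K-M median, followed through | K-M median, censored at radiotherapy |
|---|---|---|
| 6 | 6.17 to 6.94 | 5.99 to 6.01 |
| 12 | 12.17 to 13.36 | 11.98 to 12.01 |

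Following through lengthens the median by about 0.2 to 0.9 months (true median 6) or 0.2 to 1.4 months (true median 12).

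*Radiotherapy is given shortly before progression (assumed).* Ten responders progress at months 2, 4, ..., 20. With no censoring the K-M median is 10, since S(10) = 5/10. Now censor the subjects who would progress at months 6 and 8 at radiotherapy in months 5 and 7. Then S(2) = 0.90, S(4) = 0.80, S(10) = 0.80 × 5/6 = 0.667, S(12) = 0.667 × 4/5 = 0.533, S(14) = 0.533 × 3/4 = 0.400. The median becomes 14. Here it is censoring that lengthens DOR.

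**The case against.** The strongest reply is that the DOR rule already covers this. It censors at later anticancer therapy, and an exclusion criterion in Section 3.3.2 lists radiotherapy among anticancer therapies. A reader might infer from the PFS wording that DOR ignores radiotherapy altogether. The text does not support that: it leaves the matter open. The PFS sentence is also unsettled, since it too speaks of *subsequent* therapy and does not say whether palliative radiation with study drug resumed qualifies. This part of the reply stands, and the point is misalignment and silence rather than an explicit exclusion.

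A second reply is that the route is narrow. Radiotherapy is discouraged, limited in field and purpose, and preceded by a check for progression. Growth of at least 50% in a node may itself be PD, index lesion or not. This also stands and bears on frequency. It does not close rows 2 and 3 of the table.

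A third reply is that following subjects through radiotherapy is a legitimate choice of estimand, and that censoring subjects close to progression is informative. This is correct, and is why a sensitivity analysis belongs in the fix. The choice still has to be stated, and made the same way for DOR and PFS.

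Finally, the two-stage design is guidance without formal testing, and Section 8.4.7.1 refers to an SAP whose text is not in the combined document. Fuller rules may exist there; that could not be checked.

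**Conclusion.** The point holds as a gap in the analysis rules. Under the rule as written, a PR or CR completed by irradiating a non-index site counts. DOR, DoCR and DoCMR are not aligned with PFS on radiotherapy and surgery, and the status of on-study palliative radiotherapy is undefined for all of them.

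Three stronger readings are tempting but unsupported:

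- *Irradiating a non-index node can create a PR by itself.* It cannot; the 50% SPD reduction must already be present in the index lesions.
- *A 52-week DOR beside PFS censored at Week 16 is a logical contradiction.* A censored time is a lower bound, so the two results reflect inconsistent handling and should not be compared as a ratio.
- *The bias always favours the drug.* For response, the gap can only add responders. For DOR, Step 4 shows shifts in both directions.

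The 5 to 10 point ORR shift is simply 1/n on assumed stage sizes of 20 and 10. The DOR shifts rest wholly on assumed inputs. The number of affected subjects is likely to be low. The gap is worth closing because it touches co-primary endpoints in small uncontrolled cohorts and costs little to close.

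**What to change.** These are changes to analysis rules only; clinical management is untouched.

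1. **Section 3.4.3:** apply the response-evaluation cut-off to tumor-directed radiotherapy of any lesion, index or non-index.
2. **Section 8.3.2.3, Section 8.3.3.3 and the synopsis:** base BOR, ORR, CR rate and CMR rate on assessments before the first of tumor-directed radiotherapy (including on-study palliative radiotherapy), tumor-directed surgery or subsequent anticancer therapy. Appendix 6 already restricts myeloma response to assessments before new therapy, but myeloma is not in Part D.
3. **Same sections:** use one definition of censoring therapy for DOR, DoCR, Lugano DOR, DoCMR and both PFS endpoints, and state expressly that on-study palliative radiotherapy is included. Copying the PFS sentence into DOR would not be enough, because that sentence leaves the same question open.
4. **Sensitivity analysis:** repeat the duration analyses following subjects through radiotherapy, because censoring there may be informative.

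The cost is wording. Section 3.4.3 already requires radiotherapy details in the CRF and source records, with dates and anatomical site in the source. ORR may fall slightly and some responders will be censored earlier.
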